## Hepatic Flares

An ALT elevation was defined as treatment-emergent serum ALT  $> 2 \times$  baseline value and  $> 10 \times$  ULN, with or without associated symptoms. Through Week 48, ALT elevations were observed for 16 subjects (1.8%) in the TAF group and 9 subjects (2.1%) of subjects in the TDF group. Most of the events were at isolated time points within the first 8 weeks of dosing and resolved without recurrence while the subject remained on study drug. An ALT elevation that was confirmed at 2 consecutive postbaseline visits was considered an ALT flare. The incidence of these events was balanced between the treatment groups. Five subjects (0.6%) in the TAF group and 4 subjects (0.9%) in the TDF group had a treatment-emergent ALT flare. With the exception of 2 events, ALT flares occurred early in the dosing period; for 7 of the 9 subjects, the ALT flares resolved without recurrence while the subject remained on study drug.

## Metabolic Laboratory Parameters

Administration of TDF has been associated with lower fasting low-density lipoprotein (LDL) and high-density lipoprotein (HDL) as compared with other antiviral agents. As plasma TFV exposures are approximately 90% lower with TAF administration than with TDF, fasting lipid concentrations remained relatively stable through Week 48 in the TAF treatment group, while TDF administration resulted in the expected lipid-lowering TFV effect, with decreases from baseline in fasting lipid parameters observed in the TDF group. Median decreases from baseline in total cholesterol, LDL, HDL, and triglycerides were greater in the TDF group than the TAF group, with TDF subjects demonstrating reductions in all parameters at Week 48. The difference between groups in median change from baseline was statistically significant a Week 48 for total cholesterol, direct LDL, HDL, and triglycerides ( $p < 0.001$ ). Median (Q1, Q3) changes from baseline at Week 48 for fasting lipid parameters were as follows:

- **Total cholesterol:** TAF -2 (-17, 17) mg/dL; TDF -24 (-42, -6) mg/dL
- **LDL:** TAF 4 (-9, 20) mg/dL; TDF -9 (-25, 5) mg/dL
- **HDL:** TAF -3 (-10, 2) mg/dL; TDF -9 (-17, -3) mg/dL
- **Triglycerides:** TAF 6 (-13, 26) mg/dL; TDF -7 (-27, 10) mg/dL

The median (Q1, Q3) change from baseline at Week 48 in total cholesterol to HDL ratio was 0.2 (-0.1, 0.5) in the TAF group and 0.2 (-0.2, 0.5) in the TDF group (p = 0.16 for the difference between treatment groups).

Eight subjects (0.9%) in the TAF group had Grade 3 elevated fasting cholesterol; 7 of the 8 subjects had a history of hyperlipidemia and/or elevated fasting cholesterol at baseline. There were no subjects with Grade 4 elevated fasting cholesterol in the TAF group, and none with Grade 3 or 4 elevated fasting cholesterol in the TDF group. Thirty-seven subjects (4.4%) in the TAF group and 1 subject (0.2%) in the TDF group had Grade 3 elevated fasting LDL. Overall, changes in median values of total cholesterol, LDL, HDL, and triglycerides in the TAF group were not clinically relevant, and none of the subjects with Grade 3 elevations in fasting lipids had clinical AEs associated with lipid abnormalities.

### 1.3. Rationale and Risk/Benefit Assessment for this Study

While the number of liver transplants for CHB consequences is low in the United States (~350/year), in countries with high prevalence of CHB, HBV remains the most important cause of liver transplantation {Lee 2015}. Without prophylaxis, patients with CHB receiving a liver transplant have near universal re-infection of the graft {Samuel 1993}. Current practice is to treat prior and post-transplant patients with oral nucleos(t)ide polymerase inhibitors and Hepatitis B Immunoglobulin (HBIG) to prevent infection of the new liver. Study 203-0107 demonstrated in a small group of post-liver transplant patients that treatment with TDF/FTC alone was equivalent to TDF/FTC + HBIG after 72 weeks of follow-up {Teperman 2013}. With these interventions, infection of the graft has been reduced to < 10% {Katz 2010}. While practice patterns for continuation of HBIG can vary by center, all patients must remain on lifelong nucleos(t)ide analog treatment.

After receiving a liver transplant, the majority of patients develop some degree of chronic kidney disease, with over 18% having a GFR < 30 ml/min within 5 years of transplant mainly as a result of the use of calcineurin inhibitors (CNI) {Lucey 2013, Ojo 2003}. CNIs are a mainstay of immunosuppression immediately after transplantation and can lead to acute or chronic kidney injury through hemodynamic changes or direct nephrotoxic effects. While some centers reduce or eliminate CNIs from immunosuppressive regimens over time, many continue patients lifelong on CNIs. Even in those patients who stop CNIs, the renal effects are often not reversible. This persistent renal dysfunction, therefore, can complicate antiviral treatment with medications such as TDF.

For these patients who have received a liver transplant and have renal insufficiency, TAF may provide an alternative to currently used treatments by achieving viral suppression while resulting in improved safety of bone and renal parameters compared to TDF-based regimens.

#### **1.4. Rationale for Dose Selection**

A 25-mg dose of TAF was selected for use in the Phase 3 non-inferiority studies based upon the magnitude of HBV DNA decline, systemic TFV exposure, and the safety profile. In Study GS-US-320-0101, the magnitude of HBV DNA decreases observed over 28 days in subjects with CHB given TAF at doses of 8, 25, 40, and 120 mg were similar indicating a lack of dose effect; these decreases were also comparable with the TDF 300-mg dose, which is the dose of TDF approved for treatment of CHB. In subjects who received TAF 25 mg, reduced systemic TFV exposures (approximately 92%) were observed relative to those who received the TDF 300-mg dose, which is consistent with data in HIV-infected subjects who received TAF 25 mg as a single agent in Study GS-US-120-0104.

The selection of 25 mg TAF dose in this study is further supported by the results from the dedicated severe renal impairment study (GS-US-120-0108). In that study, plasma TAF exposure in subjects with severe renal impairment was less than 2-fold higher than TAF exposure in matched controls with normal renal function. For TFV, mean AUC was ~6-fold higher in renally impaired subjects as compared to matched controls. Importantly, TFV exposure was within the range of TFV exposures achieved following administration of a TDF-containing regimen in subjects with normal renal function. As such, dose adjustment of TAF in severe renal impairment was not warranted.

The PK/PD relationship between TAF plasma exposure and efficacy was also explored using data from the Phase 3 Studies GS-US-320-0108 and GS-US-320-0110. Importantly, in both studies virologic suppression (HBV DNA < 29 IU/mL) was uniform across the categories of TAF exposures, with no trends in exposure-response relationship observed.

#### **1.5. Compliance**

This study will be conducted in compliance with this protocol, Good Clinical Practice (GCP), and all applicable regulatory requirements.

## 2. OBJECTIVES

The primary objectives of this study are:

- To evaluate the safety and tolerability of TAF 25 mg QD versus TDF-containing regimens as determined by the change from baseline in eGFRCKD-EPI at Week 24
- To evaluate the efficacy of TAF 25 mg QD versus TDF-containing regimens in maintaining viral suppression at Week 24

The secondary objectives of this study are:

- To evaluate the safety of TAF 25 mg QD versus TDF-containing regimens as determined by the percent change from baseline in hip and spine bone mineral density (BMD) at Weeks 24 and 48
- To evaluate the safety of TAF 25 mg QD versus TDF-containing regimens as determined by the change from baseline in serum creatinine at Weeks 24 and 48
- To evaluate the safety of TAF 25 mg QD versus TDF-containing regimens as determined by the change from baseline in eGFRCKD-EPI at Week 48
- To evaluate the efficacy of TAF 25 mg QD versus TDF-containing regimens in maintaining viral suppression at Week 48

The exploratory objectives of this study are:

- [REDACTED]
- [REDACTED]
- [REDACTED]
- [REDACTED]

### 3. STUDY DESIGN

#### 3.1. Endpoints

##### 3.1.1. Primary Endpoints

The **primary safety endpoint** is:

- Change from baseline in eGFRCKD-EPI of TAF 25 mg QD versus TDF-containing regimens at Week 24

The **primary efficacy endpoint** is:

- Proportion of subjects with HBV DNA < 20 IU/mL at Week 24

##### 3.1.2. Secondary Endpoints

The **secondary safety endpoints** are:

- Percent change from baseline in hip and spine bone mineral density (BMD) of TAF 25 mg QD versus TDF-containing regimens at Weeks 24 and 48
- Change from baseline in serum creatinine of TAF 25 mg QD versus TDF-containing regimens at Weeks 24 and 48
- Change from baseline in eGFRCKD-EPI of TAF 25 mg QD versus TDF-containing regimens at Week 48

The **secondary efficacy endpoint** is:

- Proportion of subjects with HBV DNA < 20 IU/mL at Week 48

##### 3.1.3. Other Endpoints of Interest

The **exploratory endpoints** of this study are:

- █ [REDACTED]
- █ [REDACTED]
- █ [REDACTED]
- █ [REDACTED]
- █ [REDACTED]

[REDACTED]

[REDACTED]

[figure not shown]
[REDACTED]

[REDACTED]

### 3.2. Study Design

This is a randomized, open label study to evaluate the antiviral activity of TAF 25 mg QD versus TDF (dose per the local label) containing regimens. Approximately fifty (50) adult CHB subjects with Stage 2 or greater chronic kidney disease and have received a liver transplant will be eligible for enrollment. They will be randomized in a 1:1 ratio (A: B) to the treatment arms for 48 weeks. Approximately 40 of 50 subjects will be enrolled with  $eGFR_{CKD-EPI} < 60 \text{ ml/min/1.73m}^2$ .

Figure 3-1. Study Schema

### 3.3. Study Treatments

Approximately 50 subjects with CHB and Stage 2 or greater chronic kidney disease and have received a liver transplant will be assigned to one of the two treatment arms (A: B) for 48 weeks. Randomization will be stratified by baseline renal function ( $eGFR_{CKD-EPI} < 50 \text{ ml/ min/1.73m}^2$  and  $\geq 50 \text{ ml/ min/1.73m}^2$ ).

- **Treatment Arm A:** approximately 25 subjects administered TAF 25 mg oral daily
- **Treatment Arm B:** approximately 25 subjects to continue administration of TDF alone or in combination with other approved antivirals per local practice

### 3.4. Duration of Treatment

The duration of the study treatment is 48 weeks with an initial screening period of 45 days. Subsequent to Screening, subjects will be randomized to receive TAF or TDF alone or in combination with approved antivirals per local practice.

At Week 48, per Principal Investigator (PI) discretion, subjects will be eligible to receive TAF 25 mg daily and CCI

they will be followed for 24 weeks after the discontinuation of TAF (i.e., Treatment Free Follow-Up, TFFU) or until an alternative CHB treatment is started, whichever occurs first.

### 3.5. End of Study

The end of the study will be the last subjects' last observation or visit.

### 3.6. Biomarker Testing

#### 3.6.1. Biomarker Samples to Address the Study Objectives

The following biological specimens will be collected in this study and will be used to evaluate the association of exploratory systemic and/or tissue specific biomarkers with study drug response, including efficacy and/or adverse events and to increase knowledge and understanding of the biology of chronic hepatitis B. The specific analyses will include, but will not be limited to, the bone and renal biomarkers –such as, C-type collagen sequence (CTX) and procollagen type 1 N-terminal propeptide (P1NP), retinol binding protein and beta-2-microglobulin.

Because biomarker science is a rapidly evolving area of investigation, and adverse events in particular are difficult to predict, it is not possible to specify prospectively all tests that will be done on the specimens provided. The testing outlined below is based upon the current state of scientific knowledge. It may be modified during or after the end of the study to remove tests no longer indicated and/or to add new tests based upon the growing state of art knowledge. Samples may be stored by Gilead Sciences for a period of 15 years.

CCI

[REDACTED]

[REDACTED]

[REDACTED]

[REDACTED]

[REDACTED]

[REDACTED]

[REDACTED]

## 4. SUBJECT POPULATION

### 4.1. Number of Subjects and Subject Selection

Approximately 50 subjects, who are 18 years or older, with chronic hepatitis B, currently virally suppressed with Stage 2 or greater chronic kidney disease and have received a liver transplant. They will be randomized 1:1 to receive TAF 25 mg or continue with TDF alone or in combination with other approved antivirals for 48 weeks.

### 4.2. Inclusion Criteria

Subjects must meet all of the following inclusion criteria to be eligible for participation in this study.

- 1) Must have the ability to understand and sign a written informed consent form; consent must be obtained prior to initiation of study procedures
- 2) Adult male or non-pregnant female subjects, over 18 years of age based on the date of the screening visit
- 3) Documented evidence of chronic HBV infection prior to transplantation
- 4) Primary or secondary (re-transplant), liver alone or liver and kidney transplant recipient from deceased or living donor
- 5) Liver Transplant  $\geq$  12 weeks prior to screening
- 6) Maintained on TDF alone or in combination with other approved antivirals for HBV prophylaxis or treatment
- 7) Have been on approved HBV OAV treatment for at least 12 weeks post-transplant prior to screening, with HBV DNA  $<$  LLOQ at screening
- 8) Screening  $eGFR_{CKD-EPI} < 90$  ml/min/1.73m^2
- 9) Male subjects and female subjects of childbearing potential who engage in heterosexual intercourse must agree to use protocol specified method(s) of contraception as described in [Appendix 6](#)
- 10) Women considered of child bearing potential (see [Appendix 6](#)) must have a negative serum pregnancy test at Screening and a negative urine test at Baseline before dosing
- 11) Must be willing and able to comply with all study requirements

### 4.3. Exclusion Criteria

Subjects who meet *any* of the following exclusion criteria are not to be enrolled in this study.

- 1) Multi-organ transplant that includes heart or lung recipient (subjects who have their liver transplant as part of a liver-kidney dual transplant are eligible to enroll)
- 2) Subjects with history of de novo or recurrent hepatocellular carcinoma (HCC) post-transplant and at screening
- 3) Histological evidence of unresolved transplant rejection
- 4) Current, uncontrolled ascites, variceal hemorrhage, hepatic encephalopathy, hepatorenal syndrome, hepatopulmonary syndrome, or other signs of decompensated cirrhosis
- 5) Subjects meeting any of the following laboratory parameters at screening:
  - a) ALT > 10× the upper limit of normal (ULN)
  - b) INR > 1.5 × ULN unless the subject is stable on anticoagulant regimen affecting INR
  - c) Albumin < 3.0 g/dL
  - d) Direct bilirubin ≥ 4 × ULN
  - e) Platelet count < 50,000/mL
  - f) eGFRCKD-EPI < 15 ml/min/1.73m^2
- 6) Subjects on hemodialysis
- 7) Co-infection with HIV or HCV
- 8) Recent (within 4 weeks of Screening) episode or infection requiring systemic antibiotics
- 9) Use of any prohibited medications listed in Section 5.4 within 28 days of the Baseline/Day 1 visit
- 10) Malignancy within 5 years prior to screening, with the exception of specific cancers that are cured by surgical resection (e.g., basal cell skin cancer, etc) or hepatocellular carcinoma. Subjects under evaluation for possible malignancy are not eligible
- 11) Significant cardiovascular, pulmonary, or neurological disease
- 12) Use of investigational agents within 3 months of screening, unless allowed by the Sponsor
- 13) Use of any prohibited concomitant medications as described in [Table 5-1](#)

- 14) Current alcohol or substance abuse judged by the investigator to potentially interfere with subject compliance
- 15) Known hypersensitivity to study drugs, metabolites or formulation excipients
- 16) Lactating females or those who may wish to become pregnant during the course of the study

## **5. INVESTIGATIONAL MEDICINAL PRODUCTS**

### **5.1. Randomization, and Treatment Codes**

The randomization will be performed via an Interactive Voice Response System (IVRS) or Interactive Web Response System (IWRS), whereby study treatment will be assigned to subjects according to the randomization schedule. A unique subject number will be provided during randomization. Eligible subjects (n = 50) will be randomized in a 1:1 ratio to receive either TAF or continue on TDF alone or in combination with other approved antivirals for 48 weeks. Randomization will be stratified by baseline renal function (eGFRCKD-EPI < 50 ml/min/1.73m^2 and ≥ 50 ml/min/1.73m^2).

### **5.2. Description and Handling of Tenofovir Alafenamide (TAF)**

#### **5.2.1. Formulation**

##### **5.2.1.1. Tenofovir Alafenamide (TAF) Tablets**

TAF 25 mg tablets contain 28 mg of tenofovir alafenamide fumarate, which is equivalent to 25 mg of tenofovir alafenamide (TAF). The tablets are yellow, round-shaped, and film-coated. The tablets are debossed with “GSI” on one side and “25” on the other side. In addition to the active ingredient, each film-coated tablet contains the following inactive ingredients: lactose monohydrate, microcrystalline cellulose, croscarmellose sodium, magnesium stearate, polyethylene glycol, polyvinyl alcohol, talc, titanium dioxide, and yellow iron oxide.

#### **5.2.2. Packaging and Labeling**

TAF tablets are packaged in white, high density polyethylene (HDPE) bottles. Each bottle contains 30 tablets and a silica gel desiccant and polyester material. Each bottle is enclosed with a white, continuous-thread, child-resistant polypropylene screw cap fitted with an induction-sealed, and aluminum-faced liner.

Study drug(s) to be distributed to centers in NZ and other participating countries shall be labeled to meet applicable requirements of local regulations.

#### **5.2.3. Storage and Handling**

Study drug TAF should be stored at controlled room temperature of 25°C (77°F); excursions are permitted between 15°C and 30°C (59°F and 86°F). Storage conditions are specified on the label. Until dispensed to the subjects, all bottles of study drugs should be stored in a securely locked area, accessible only to authorized site personnel.

To ensure the stability and proper identification, study drug(s) should not be stored in a container other than the container in which they were supplied.

Consideration should be given to handling, preparation, and disposal through measures that minimize drug contact with the body. Appropriate precautions should be followed to avoid direct eye contact or exposure when handling.

### 5.3. Dosage and Administration of TAF

Subjects will be randomly assigned (1:1) to receive one of the following treatments:

- **Treatment Arm A:** approximately 25 subjects administered TAF 25 mg QD
- **Treatment Arm B:** approximately 25 subjects to continue administration of TDF alone or in combination with other approved antivirals alone or in combination with other approved antivirals per local practice

After 48 weeks, subjects in treatment arms A and B will be eligible to receive TAF 25 mg daily

CCI

It is preferred that subjects take their study drug according to a morning dosing schedule; however, evening dosing is allowable.

TAF tablets are to be administered orally with food, taken at approximately the same time each day.

### 5.4. Prior and Concomitant Medications

Concomitant/previous medications **taken within 30 days of screening**, up to and including the date of the visit 4 weeks after discontinuation of study treatment, need to be recorded in the source documents and eCRFs.

The following medications are **prohibited during the screening period and for a minimum of 28 days prior to the Day 1** visit through the end of treatment:

- Investigational agents or devices for any indication
- Nephrotoxic agents (e.g., aminoglycosides, amphoterecin B, vancomycin, cidofovir, foscarnet, cisplatin, pentamidine)
- Probenecid
- Agents that reduce renal function or compete for active tubular secretion with tenofovir (e.g., cidofovir, acyclovir, valacyclovir, ganciclovir, valganciclovir)
- Systemic chemotherapeutic agents

Treatment-experienced subjects (defined as subjects meeting all entry criteria [including HBV DNA and serum ALT criteria] and with  $\geq 12$  weeks of previous treatment with any nucleoside or nucleotide analogue) receiving oral antiviral treatment at Screening must continue their treatment regimen until the time of randomization/Baseline/Day 1, when it will be discontinued.

Concomitant use of certain medications or herbal/natural supplements (inhibitors or inducers of drug transporters i.e., P-gp) with study drug(s) may result in PK interactions resulting in increases or decreases in exposure of TAF.

**Examples of representative medications which are prohibited or to be used with caution from 21 days prior to Day 1 through the end of treatment are listed below:**

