**Study Design:**

This is a randomized, open-label, single center Phase 2 study to evaluate the safety and efficacy of TAF 25 mg QD versus TDF in adult chronic hepatitis B infection (CHB) subjects with Stage 2 or greater chronic kidney disease and have received a liver transplant.

Approximately 50 subjects will be randomized in a 1:1 ratio to either continue current treatment regimen with TDF alone or in combination with other approved antivirals or to receive TAF 25 mg PO daily. Approximately 40 of 50 subjects will be enrolled with  $eGFR_{CKD-EPI} < 60$  ml/min/1.73m^2.

Randomization will be stratified by baseline renal function ( $eGFR_{CKD-EPI} < 50$  ml/min/1.73m^2 and  $\geq 50$  ml/min/1.73m^2)

- **Treatment Arm A:** approximately 25 subjects administered TAF 25 mg oral daily
- **Treatment Arm B:** approximately 25 subjects to continue administration of TDF alone or in combination with other approved antivirals as per local practice

CCI [REDACTED]

The primary analysis will occur at Week 24 with the primary efficacy endpoint being the maintenance of viral suppression (HBV DNA < 20 IU/mL).

CCI  
[Redacted]

Number of Subjects Planned: Approximately 50

Target Population: Adult subjects with CHB who are currently virally suppressed, receiving TDF alone or in combination with other approved antivirals as per local practice, with Stage 2 or greater chronic kidney disease and have received a liver transplant.

Duration of Treatment: TAF will be administered orally once daily for 48 weeks for subjects in Treatment Arm A. Subjects in Treatment Arm B will continue on TDF alone or in combination with other approved antivirals. CCI  
[Redacted]

Diagnosis and Main Eligibility Criteria: **Inclusion Criteria**

Subjects must meet **all** of the following **inclusion criteria** to be eligible to participate in the study:

- 1) Must have the ability to understand and sign a written informed consent form; consent must be obtained prior to initiation of study procedures
- 2) Adult male or non-pregnant female subjects, over 18 years of age based on the date of the screening visit
- 3) Documented evidence of chronic HBV infection prior to transplantation
- 4) Primary or secondary (re-transplant), liver alone or liver and kidney transplant recipient from deceased or living donor
- 5) Liver Transplant  $\geq$  12 weeks prior to screening

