### 6.1. Subject Enrollment and Treatment Assignment

It is the responsibility of the investigator to ensure that subjects are eligible to participate in the study prior to enrollment. Once consent has been obtained, all screening tests and procedures have been completed, and study eligibility has been confirmed, subjects will be randomized within 45 days using an IVRS/IWRS. Subjects will receive study drugs within their assigned treatment group as described in Section 3.2. Candidates who fail to meet eligibility criteria by screening evaluations may be re-screened once after the initial screen if there is a reasonable expectation that the candidate will be eligible after repeat screening.

Retesting of an exclusionary laboratory value during the Screening period is permitted only if in the Principal Investigator's opinion, the retest value will be within accepted parameters; if the initial value was deemed to be inaccurate, inconsistent with the subject's previous result(s); in error (e.g. mishandled sample); or due to an extenuating circumstance.

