1.2. Study Design

This is a randomized, open-label, single center Phase 2 study to evaluate the safety and efficacy of TAF 25 mg QD versus TDF in adult chronic hepatitis B (CHB) infection subjects with Stage 2 or greater chronic kidney disease and have previously received a liver transplant.

Treatment Groups

Approximately 50 subjects will be randomized 1:1 to either continue current treatment regimen with TDF (alone or in combination with other approved antivirals) or to receive TAF 25 mg orally daily. Approximately 40 of 50 subjects were to be enrolled with $eGFR_{CKD-EPI} < 60$ ml/min/1.73m². Randomization was stratified by screening renal function ($eGFR_{CKD-EPI} < 50$ ml/min/1.73m² and ≥ 50 ml/min/1.73m²)

- **Treatment Arm A:** approximately 25 subjects administered TAF 25 mg oral daily
- **Treatment Arm B:** approximately 25 subjects to continue administration of TDF alone or in combination with other approved antivirals as per local practice

Key Eligibility Criteria

Subjects were to have met the following key eligibility criteria:

- Documented evidence of chronic HBV infection prior to transplantation
- Primary or secondary (re-transplant), liver alone or liver and kidney transplant recipient from deceased or living donor
- Liver Transplant ≥ 12 weeks prior to screening
- Maintained on TDF alone or in combination with other approved antivirals for HBV prophylaxis or treatment
- Have been on approved HBV oral antiviral (OAV) treatment for at least 12 weeks post-transplant prior to screening, with HBV DNA $<$ lower limit of quantitation (LLOQ) at screening
- Screening $eGFR_{CKD-EPI} < 90$ ml/min/1.73m²

Study Periods/Phases

The duration of the study treatment is 48 weeks with an initial screening period of 45 days. Subsequent to Screening, subjects will be randomized to receive TAF or TDF alone or in combination with approved antivirals per local practice.

CCI

If subjects CCI choose to not continue or discontinue TAF prematurely, they will be followed for 24 weeks after the discontinuation of study treatment (ie, Treatment Free Follow-Up, TFFU) or until an alternative CHB treatment is started, whichever occurs first. In this SAP, the first 48 weeks of study treatment is referred to as randomized phase, CCI

Schedule of Assessments

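### Protocol Section 5.4 discontinues the screening oral antiviral regimen on Day 1 without naming an arm, which contradicts Arm B's assignment to continue it

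*Protocol*

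**What the plan says.** Protocol Section 5.4 governs prior and concomitant medication. It defines treatment-experienced subjects as those who meet the entry criteria and have had 12 weeks or more of any nucleoside or nucleotide analogue. It then says that such subjects "receiving oral antiviral treatment at Screening must continue their treatment regimen until the time of randomization/Baseline/Day 1, when it will be discontinued". No arm is named and no exception follows.

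Eligibility is set in Section 4.2. Criterion 6 reads "Maintained on TDF alone or in combination with other approved antivirals for HBV prophylaxis or treatment". Criterion 7 begins "Have been on approved HBV OAV treatment for at least 12 weeks post-transplant prior to screening".

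The assigned treatments are described consistently elsewhere:

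- The synopsis randomizes subjects to "either continue current treatment regimen with TDF alone or in combination with other approved antivirals or to receive TAF 25 mg PO daily". SAP Section 1.2 has the same choice: "either continue current treatment regimen with TDF (alone or in combination with other approved antivirals".
- Section 3.3 describes Arm B as "approximately 25 subjects to continue administration of TDF alone or in combination with other approved antivirals per local practice".
- Section 5.1 says that subjects not given TAF "continue on TDF alone or in combination with other approved antivirals for 48 weeks".
- Sections 4.1 and 5.3 of the protocol, the randomization paragraph of SAP Section 1.2, and SAP Section 3.7.1 also have the control group carry on with TDF.

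**The concern.** Section 5.4 and the treatment-assignment sections speak of the same thing, the antiviral regimen a subject is taking at Screening, and of the same moment, Day 1. One says that it stops. For Arm B the others say that it goes on. A site that follows the assignment in Arm B is therefore out of line with the letter of Section 5.4.

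The subject matter is the reason to tidy this up. Section 1.3 of the protocol explains that graft reinfection is close to universal without prophylaxis and that nucleos(t)ide therapy is needed for life after transplant. Continued TDF is also the comparator for both primary endpoints. A rule on stopping antivirals in this population should say whom it applies to.

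**Working it through.** No power, alpha or effect-size calculation bears on this point, and both documents state that no formal sample size calculation was done. The check is a comparison of texts.

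1. **Whom does the Section 5.4 rule cover?** Its definition needs 12 weeks or more of a nucleoside or nucleotide analogue, and the rule applies to those on oral antivirals at Screening. Criterion 6 puts every subject on TDF, itself a nucleotide prodrug. Criterion 7 gives every subject 12 weeks or more of oral antiviral treatment before Screening. So the rule covers all of about 50 planned subjects, in both arms.

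2. **What does it require?** The regimen taken at Screening ends at randomization/Day 1.

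3. **What does each arm's assignment require?**
   - Arm A: TAF replaces the earlier regimen. Section 5.4 agrees.
   - Arm B: the synopsis and SAP Section 1.2 keep subjects on their current regimen. Section 5.4 says the opposite.

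4. **How many subjects does the conflict touch?** About 25 of 50, or 25/50 = 50%. This is only the 1:1 allocation. It shows the reach of the wording and says nothing about harm or bias.

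5. **Does anything elsewhere limit or correct the sentence?** Section 6.1 says "Subjects will receive study drugs within their assigned treatment group as described in Section 3.2", and Section 6.2.2 starts study drug on the day of the Baseline visit. Section 7.5.5.1 sets TDF dose adjustments during the study. SAP Section 3.7.1 gives the TDF group its own Study Day 1 rule because those subjects are already taking TDF. All of these confirm the intent. None restricts Section 5.4 to Arm A. Where rules differ by arm, the protocol can say so: Sections 7.5.5.1 and 7.5.5.2 are labelled separately for TDF and TAF.

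6. **Could the sentence simply be deleted?** No. The visible text has no other explicit instruction that Arm A subjects stop their earlier HBV drugs. Some are likely to enter on combinations, since SAP Section 5.2 tabulates lamivudine use at Day 1. Arm A needs the sentence, so it should be restricted and kept.

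**The case against.** The strongest reply is that Section 5.4 concerns prior and concomitant medication, and that in Arm B TDF changes status on Day 1: it ends as pre-study medication and resumes as randomized treatment. Some text leans that way. The synopsis lists open-label TDF as reference therapy. Section 3.4 has subjects randomized to receive TAF or TDF. Section 7.5.5.1 at one point calls TDF study drug. SAP Section 3.7.1 starts the TDF group's clock at the first dose on or after the Baseline visit. On this reading there is no conflict.

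The reading is reasonable, but no text states it, and the synopsis describes Arm B as keeping its current regimen. Nor does the visible text describe a replacement TDF supply: Section 5.2 covers TAF only, the reference therapy follows local practice, and SAP Section 4.2.2 counts tablets for the TAF group only.

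The second reply is that nobody would be misled, because the sections that define treatment, including Section 5.3 immediately before 5.4, all say that Arm B continues. This stands, and it sets the severity.

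A reader might infer from the literal wording that control subjects would lose their prophylaxis or have a treatment gap, or that the comparator would disappear. The documents do not support that. It would require obeying one sentence against every description of Arm B and against the on-study TDF dosing rules. SAP Section 2.1.1 reports that the data monitoring committee found no safety concern that called for changing the study, and SAP Sections 2.1.2 and 2.1.3 report the Week 24 and Week 48 analyses as done. No endpoint, analysis set or estimate is shown to be affected.

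**Conclusion.** The inconsistency is real. Section 5.4 as written ends on Day 1 a regimen that about half the subjects are assigned to continue, and no visible text corrects it. It is a low-end minor drafting error in an operative rule. The intent is clear and misapplication is unlikely.

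This rests on two assumptions: that enrolled subjects met criteria 6 and 7, so that all fall under the definition, and that no redacted text limits the sentence to Arm A. By the time of the SAP the randomized phase was complete, so the remaining value of a correction is an accurate record and clean wording for reuse.

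**What to change.** Replace the sentence in Section 5.4 with wording such as:

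*For subjects randomized to TAF (Arm A), all prior oral HBV antivirals are discontinued on Day 1, when TAF starts. Subjects randomized to Arm B continue their TDF-containing regimen per Section 3.3, subject to the discontinuation and toxicity rules in Sections 6.6 and 7.5.*

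The requirement to stay on the existing regimen up to Day 1 can remain for both arms. Two details matter. The word oral should stay, because Section 1.3 notes that hepatitis B immunoglobulin practice varies by center and Section 5.4 does not address it. The cross-reference for Arm B should cover Section 6.6 and the whole of Section 7.5, because the renal rules in 7.5.5 alone would leave out virologic failure, pregnancy, subject request and the general toxicity and ALT-flare rules.

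The cost is two sentences of protocol text. Sample size, visits, data collection and the planned analyses do not change.
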